Recruitment: We will review a register of BMT patients at the CHC who have consented to be contacted about research studies. We will contact patients who meet inclusion criteria and their providers. We will also extract data quarterly from electronic medical records to identify patients who have started buprenorphine treatment within the last 12 weeks. We will not contact patients directly, but instead, we will contact their primary care providers who will inform patients about the study and give the research team permission to contact patients. We will send potential participants letters from their PCP inviting them to participate in the study. Fliers describing the study will be posted at the CHC. The study will be described at staff meetings.

Randomization: A research assistant will contact and meet with eligible patients at the CHC to describe the study. At enrollment, written informed consent will be obtained, and forms to release medical records will be signed. Randomization will occur in blocks of 16 via a sealed envelope with allocation (G-BMT vs. TAU).

Screening Procedures: Potential participants who contact the study coordinator will be screened for inclusion and exclusion criteria. The study coordinator will also call potential study participants who are identified by PCPs or on the BMT register. The study coordinator will administer a three part screener by phone or in person. For patients referred to the study by their PCP, the study coordinator will check records to confirm: receipt of BMT for ≥ 12 weeks and documentation of illicit opioid use in the prior 6 months. The study coordinator will elicit oral informed consent based on a standard script and then ask seven screening questions to confirm receipt of buprenorphine, ongoing illicit opioid use, interest in group treatment, pregnancy, and other study inclusion/exclusion criteria. We will not be conducting pregnancy tests. To screen for unstable mental health conditions, the research coordinator will administer the suicidality, PTSD/violence risk, and psychosis modules from the MINI 6.0. If criteria for any of these conditions are met or if the research coordinator expresses concerns about group suitability, [name] will make a clinical assessment in person prior to study enrollment.

Research Visits: The research assistant will meet with all participants at enrollment and at 2, 4, 6, 8, 12, and 16 weeks

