following initiation of G-BMT or TAU. Research visits, which are separate from group medical visits or individual provider visits, will occur in a private room at the CHC and participants will receive \$25 compensation following completion of research activities. At each visit, computerized interviews and urine will be collected. Six months after enrollment, medical record data will be extracted for additional data collection.

Clinical Visits:

G-BMT intervention: The G-BMT intervention will begin with 8 weekly 90-minute group medical visits after a block of 8 participants has been randomized to the intervention arm. The anticipated protocol for G-BMT is described below. Urine drug tests will be collected at each group visit and will be used as a secondary study outcome and to modify management of addiction treatment as described.

The G-BMT intervention will include group medical visits where 8-10 patients simultaneously receive care from a multidisciplinary team of a generalist physician and a behavioral specialist (i.e. clinical social worker or psychologist). Patients will be expected to attend each 90 minute session, sign a confidentiality agreement, and will receive BMT prescriptions (one week supplies) only at the end of sessions (not in between visits). We anticipate that the G-BMT intervention will include: 1) BMT-related education, 2) instruction on self-management skills, 3) peer support, and 4) individual medical management.

Buprenorphine-related education: Topics will include buprenorphine pharmacology, neuroanatomic changes that occur with addiction, HIV risk reduction, and other topics related to opioid addiction. The generalist physician will deliver 15 minutes of information per visit.

Self-management skills: Empowering participants for self-management of their addiction will occur through an adapted cognitive behavioral intervention. Each visit will begin with completion of *self-assessment forms*, which will help participants set their own buprenorphine treatment goals, record progress toward goals, and privately report relapse. The behavioral specialist will provide 20-25 minutes of instruction at each visit.

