Treatment as usual: Participants randomized to TAU will continue to receive BMT from their PCPs based on a standardized BMT intensification protocol. Prior to the study, PCPs at the CHC will receive one hour of training on BMT intensification. The protocol will require that all BMT patients with persistent opioid abuse receive at least monthly visits with urine drug tests collected at each visit. For participants randomized to TAU, PCPs will receive an automated e-mail reminder about the following protocol. After one urine drug test is positive for opioids, PCPs will increase the frequency of visits to twice monthly with referral for behavioral counseling. After two consecutive positive tests, PCPs will increase visit frequency to weekly. After three consecutive positive tests, PCPs will refer to an addiction specialist or opioid treatment program. We will measure frequency of BMT visits, referral for behavioral counseling and referral to opioid treatment programs during the study. We will determine *observed intensity* of BMT (defined below) for exploratory analyses of treatment outcomes.

Participant tracking: To facilitate tracking participants over the 16 week follow-up period we will use tracking procedures that we developed to retain drug users in our previous research studies, in which we have had an 85% retention rate over 6-month follow-up. On Locator Forms, we will record information about: 1) participants' address and phone number; 2) contact information of participants' family members, friends, case managers, physician, pharmacy, and drug treatment program; and 3) locations where participants hang out.

Data sources and measures: A complete list of measures is listed in Table 1.

Urine Drug Testing: Research visits will include urine drug test collection, which will be used for the primary outcome (both G-BMT and TAU participants will have an equal number of research visits and urines). Urine drug tests collected during G-BMT and TAU medical visits (*clinical drug tests*) will be used for secondary outcomes.

Testing will include opiates, oxycodone, buprenorphine, methadone, cocaine, and benzodiazepines.

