Interview data will be collected via audio computer-assisted self-interview (ACASI) technology at baseline and during research visits 2, 4, 6, 8, 12, and 16 weeks following enrollment. *Urine samples* will be collected for drug testing at baseline and during research visits 2, 4, 6, 8, 12, and 16 weeks following enrollment. Urine drug tests will be conducted at the community health center using commercially available rapid urine drug test. At these research visits, the RA will ask subjects to provide a urine specimen in a private bathroom while the RA stands outside the door listening for tampering. Results of urine drug tests will be recorded on a standardized paper form only using the participants study ID and not other personal identifiers. *Feasibility* measures will be collected by the research assistant (RA) who will observe, time, and collect written intervention materials (e.g. self-assessment forms) from group visits. We plan to run 5 cycles of group visits, therefore, these field notes will be marked with the cycle number and group visit number but will not contain participant identifiers. *Written intervention materials* will be marked only with a study ID and transported directly to the research offices following weekly meetings between [name] (PI) and the research team. Materials will be stored in locked file cabinets. *Audio recordings* of each group visit and qualitative interviews will be collected by the RA using a digital audio-recording device. After each group visit or qualitative interview, audio recordings will be transferred to a single password protected encrypted computer and then erased from the recording device. Audio recordings will be uploaded to a secure internet portal for professional transcription and then will be transcribed with blinding of any references to personal identifiers.

Medical record data will be electronically extracting from Montefiore's centralized clinical database, and will include buprenorphine prescription data, and data on clinical visits (medical and counseling) and chronic health conditions. The electronic file will be created by Montefiore health technology staff, emailed to the PI in a password protected file, and saved on an encrypted password protected computer.

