Validity and integrity: For interview data, participants will enter data directly into a laptop computer, but the RA will be available to answer any questions about interview. We will develop the computerized ACASI interviews so that there are limits on the potential responses that can be entered. The research assistant will also record and intervene if participants appear to be responding to questions too rapidly or in a mechanical way, which may indicate a problem with data integrity. Urine drug tests will be conducted at the community health center using commercially available rapid urine toxicology tests. To ensure validity and integrity of the urine samples, all urine samples will be collected by research staff. The RA will ensure that participants will not enter the private bathroom with jackets, purses, or any personal affects. The RA will stand outside of the bathroom to listen for possible tampering. In addition, research staff will ensure that the urine is warm (cold urine could indicate adulteration). Feasibility measures and written intervention materials will be collected using standardized paper forms by a trained research assistant. Protocol manuals and training of research assistants will include detailed discussion of the importance of recording reliable, valid data when observing group visits. [name] will review 25% of audio recordings from group visits to confirm fidelity to the intervention manual.

Accuracy and completeness: To ensure completeness of attendance at group visits, participants will receive a round-trip transit pass (worth \$5.50), which will facilitate transportation to and from the community health center. To ensure completeness of data collection, we will provide compensation (\$25) for each of the six research visits when interview and urine samples will be collected.

To ensure accuracy and completeness of interview data, we will program the ACASI interview such that participants will be required to answer each question before they can move on to the next question. If participants would like to skip a question, they will be able to inform the RA who will then advance the computer to the next question. Accuracy will be facilitated by using a touch screen computer (rather than a keyboard or mouse) which is likely to reduce participant errors. Data entry will not be required for interview data because participants directly enter their answers into the computer.

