Einstein IRB for review and approval prior to implementation. Any protocol deviations will be reported to the Einstein IRB within 10 days on a standard IRB protocol deviation reporting form, and corrective action will be implemented as necessary. Reports to the data safety monitoring committee will occur every six months and will include information about any amendments to the protocol and any protocol deviations. Amendments to the protocol will be reported to the Program Officer at NIDA in annual progress reports.

Trial stopping rules: Interim analysis of the data will be conducted when 50% of the sample has accrued (N = 40). If the results show overwhelming, statistically significant differences in opioid abstinence or retention in treatment between the intervention and TAU arms, the study will be stopped. If we find that buprenorphine treatment discontinuation or serious adverse events are significantly more likely in the TAU arm compared to the G-BMT arm (e.g., if primary care providers stop buprenorphine treatment because of persistent opioid abuse), the randomized study will be halted. If the study is halted due to the results of an interim analysis, the study may still continue as a one-arm trial (e.g., all subjects will participate in the G-BMT intervention until 80 participants have enrolled) in order to collect additional process measures on conducting group visits.

Interim analyses will be conducted by [name] with close feedback from the biostatistician. The research team, in collaboration with the DSMC and the Program Officer of NIDA will review all pertinent data to determine whether to continue accrual. A decision to stop the study may be made at any time that the research team and DSMC agrees that an unacceptable type and/or frequency of adverse events has been observed. [name] will report the decision to terminate the study to the DSMC, IRB and NIDA within 48 hours of this determination. He will submit a narrative description of the reasons for early termination of the study to the IRB and NIDA within 10 days.

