Continuing BMT despite ongoing opioid abuse: Participants with three consecutive urine drug tests that are positive for opioids during group medical visits will be offered facilitated referral to methadone maintenance treatment program; however, some may refuse referral. In the G-BMT intervention arm, the research team will meet to discuss the risks and benefits of continuing BMT and participation in group medical visits. In the TAU arm, continuation of BMT will be up to the prescribing physician. If there is concern that risks of continuing treatment outweigh the potential benefits, the participant will be removed from the trial and referred to an

addiction specialist.

Burden of BMT intensification: We will collect data on adherence to medication and visits as a feasibility measure, and we will monitor treatment, after 50% of the sample has accrued.

Potential benefits for participants: Group visits have the potential to improve rates of opioid abstinence thereby reducing HIV risk behaviors and overdose risk. Our preliminary work on buprenorphine group visits has demonstrated that they are highly valued, therefore, other benefits, such as reductions in depressive symptoms or distress, may lead to improved health status.

Collection of AEs and SAEs: Because the research visits will include computerized interviews and urine collection, and the G-BMT intervention will include group counseling and buprenorphine education, participants are likely to incur no more than minimal risk of AEs. However, if AEs occur, they are likely to include psychological distress. AEs will be collected by members of the research team as they conduct research visits or group visits, and will be reported to [name] either immediately (for serious AEs) or during regular weekly project meetings (for non-serious AEs). Serious AEs could include death, life-threatening adverse reaction, inpatient hospitalization, persistent disability, or an event jeopardizing the participant's health.

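### Adverse events are collected at more contacts in G-BMT than in TAU, with no common look-back or record source, so SAEs may be under-recorded in TAU and the halting rule for a TAU excess blunted

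*Combined protocol and SAP*

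**What the plan says.** Trial Safety, Collection of AEs and SAEs, gives the only operational statement of how events are found: "AEs will be collected by members of the research team as they conduct research visits or group visits".

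The two kinds of visit are distributed as follows.

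- **Research visits, both arms.** Under Research Visits: "The research assistant will meet with all participants at enrollment and at 2, 4, 6, 8, 12, and 16 weeks". Accuracy and completeness refers to "each of the six research visits when interview and urine samples will be collected". These visits are separate from group and individual clinical visits.
- **Group visits, G-BMT only.** Under Clinical Visits: "The G-BMT intervention will begin with 8 weekly 90-minute group medical visits". The research assistant attends them (Intervention Materials). The part of Trial Safety on stress from group participation adds review of session recordings and regular meetings with the study clinicians about distress, again for group sessions only.

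TAU patients are treated by their own primary care physicians, who are given no AE-reporting role. Table 1 has no AE, overdose or hospitalization item. Under Data acquisition and transmission, the record extract "will include buprenorphine prescription data, and data on clinical visits (medical and counseling) and chronic health conditions".

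Trial stopping rules, and again Interim analysis of efficacy data, provide that the randomized study is halted if "buprenorphine treatment discontinuation or serious adverse events are significantly more likely in the TAU arm compared to the G-BMT arm". The first of these sections sets the interim look at 40 participants.

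**The concern.** The plan already recognises that unequal observation distorts a comparison. For the primary urine outcome it points out that "both G-BMT and TAU participants will have an equal number of research visits and urines", and it moves clinical urines to secondary outcomes. Safety has no such protection.

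If events are noticed more readily where research staff see patients more often, the same true event rate gives a lower recorded rate in TAU. Two things follow. A real TAU excess of SAEs, which is what the halting rule looks for, becomes harder to see. And G-BMT may look less safe than it is. Overdose, which the plan hopes to reduce ("thereby reducing HIV risk behaviors and overdose risk"), has no scheduled measure in either arm.

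**Working it through.** **1. The plan's own count.** The listed weeks 2, 4, 6, 8, 12 and 16 give 6 research visits after baseline. This reproduces the six stated under Accuracy and completeness.

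**2. Scheduled collection contacts after baseline.**

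| Period | G-BMT | TAU |
|---|---|---|
| Weeks 1-8 | 4 research + 8 group = 12 | 4 |
| Weeks 9-16 | 2 | 2 |
| Total | 14 | 6 |

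The ratio is 14/6 = 2.33. Research weeks 2, 4, 6 and 8 are also group weeks, so distinct contact weeks are 8 + 2 = 10 against 6. With an assumed 85% research attendance (5.1 visits per arm) and 50% to 85% group attendance (4.0 to 6.8 visits), the ratio is 9.1/5.1 = 1.8 to 11.9/5.1 = 2.3.

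**3. From contacts to recorded events.** The documents state no recall window, so one has to be assumed. Suppose an event is recorded only if a contact follows within the window, true rates are equal, and all visits are attended. The apparent ratio is then the ratio of days covered.

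| Assumed window | Period | G-BMT | TAU | Ratio |
|---|---|---|---|---|
| 7 days | Weeks 1-8 | 8×7 = 56 of 56 | 4×7 = 28 of 56 | 2.0 |
| 7 days | Weeks 1-16 | 56 + 2×7 = 70 of 112 | 28 + 2×7 = 42 of 112 | 1.7 |
| 14 days | Weeks 1-8 | 56 of 56 | 4×14 = 56 of 56 | 1.0 |
| 14 days | Weeks 1-16 | 56 + 2×14 = 84 of 112 | 56 + 2×14 = 84 of 112 | 1.0 |

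If events are recalled back to the previous visit, the ratio is 1.0 throughout.

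**4. The halting rule at the interim.** The inputs are N = 40, an assumed 20 per arm, and Fisher's exact test at two-sided 0.05 (the plan names neither test nor level).

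- 5 against 0 SAEs: p = 2 × C(20,5)/C(40,5) = 2 × 15,504/658,008 = 0.047.
- 4 against 0 SAEs: p = 2 × C(20,4)/C(40,4) = 2 × 4,845/91,390 = 0.106.

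One unrecorded TAU event can therefore decide whether the rule is met.

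**5. Illustration by exact binomial enumeration, 20 per arm.** All event and detection rates are assumptions; the documents give none.

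| Detection, TAU / G-BMT | True risk 40% TAU, 10% G-BMT: TAU excess flagged | True risk 20% in both: TAU excess flagged | True risk 20% in both: G-BMT excess significant |
|---|---|---|---|
| 100% / 100% | 49% | 1.1% | 1.1% |
| 85% / 95% | 35% | 0.7% | 1.7% |
| 70% / 95% | 21% | 0.3% | 2.9% |
| 50% / 95% | 8% | 0.1% | 6.1% |

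Under-recording in TAU makes a true TAU excess harder to flag and a false one rarer.

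**The case against.** **Size.** A reader might infer from 14 against 6 contacts that SAEs will be recorded at about twice the rate in G-BMT. The documents do not support that. The twofold figure needs the 7-day window. Deaths, hospitalizations and lasting disability would normally still be reportable at the next research visit, and a group session is not shown to yield as much as a private interview. This stands, and the size has to be left open. Short-lived distress, the event type the plan thinks most likely, is where a gap is most plausible. The depression scale at weeks 0, 8 and 16 in both arms does not record events.

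**False halt.** A reader might also fear that the imbalance could stop the trial wrongly. The rule acts on a TAU excess, and the bias runs the other way, so it can only blunt that rule.

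**Dropouts.** It is tempting to say that people who stop attending vanish from the SAE count. Leaving the groups or TAU care does not end research visits, and locator tracking covers all participants. The gap is confined to those who miss research visits as well. Tracking names no SAE source for them.

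**Other safeguards.** The monitoring plan promises ongoing monitoring by staff, provides for any distressed participant to be brought to an investigator's attention, and requires any SAE to be reported whether or not it is related. Those provisions apply to both arms, but they say what happens once an event is known. None says how a TAU event becomes known. The extract of clinical visits might include hospital or emergency encounters; the text does not say so.

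**Consequences.** The research team and monitoring committee may stop at any time for adverse events without a by-arm test. Even perfect detection flags the assumed 40% against 10% only 49% of the time, so sample size is the larger limit. The analysis sections plan no by-arm AE analysis, and what the power section carries to a larger trial is an effect size. All of this narrows the point, but the SAE limb of the halting rule is a by-arm comparison and is still exposed.

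**Conclusion.** The concern holds as one of unequal ascertainment with a likely direction and unknown size. As written, collection contacts are 14 against 6 (10 against 6 distinct weeks), all of the difference lies in weeks 1-8, and no stated source evens it out. The likely effect is relative under-recording in TAU. That would weaken the SAE limb of the halting rule, where at an assumed 20 per arm the threshold lies between 4 and 5 events against none, and could make G-BMT look less safe.

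The apparent ratio at equal true rates runs from about 1.0 (recall of 14 days or more) to about 2.0 (weeks 1-8, 7-day window). It is probably small for deaths and hospitalizations and larger for distress. The treatment-discontinuation limb of the same rule can be judged from prescription records and is not affected. Because the plan uses SAEs to decide whether randomization continues, and the remedy is cheap, this should be corrected.

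**What to change.** 1. At each of the six research visits, in both arms, ask the same fixed questions on overdose, emergency visit, hospitalization and distress needing care, covering the time since the last completed research visit.
2. After a missed visit, ask the participant directly by phone or at the next visit. Disclose nothing to Locator Form contacts; breach of confidentiality is the first risk the protocol lists.
3. State that the planned record extract includes hospitalizations, emergency visits and deaths for every randomized participant.
4. Record the source of each event.
5. Base the primary by-arm SAE comparison, including the one in the halting rule, on events ascertainable from the sources common to both arms. A group-visit event that those sources also confirm counts. Show the all-source count by arm beside it, so that no known SAE is dropped.
6. Keep reporting SAEs first seen at group visits within 48 hours, as now.

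The cost is a few questions at visits already scheduled, some extra extract fields, and occasional calls. Recorded counts may rise, mainly in TAU; the monitoring committee should be told to expect this.
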